8.4. Data Collection

Refer to *Appendix 1 (Schedule of Activities)* for detailed timing and frequency of the below activities:

- Informed consent
- Demographic and contact information
- Oxygen saturation by pulse oximetry
- Pregnancy test (collected only at baseline)

٠

- Hemoglobin, creatinine, liver function test (AST, ALT, Bilirubin) at baseline, day 7, day 14 and during long term follow up visits at 6mo, 12mo and 24mo (If the patient remains hospitalized after 14 days, or the drug is discontinued for any reason, creatinine and hemoglobin lab values will be collected for up to 2 days following the last dose, again ceasing upon discharge.)
- Height, weight, BMI
- Eligibility, at baseline
- Randomization
- Blood biomarkers (during hospitalization only) \circ Baseline, Day 7 and Day 14 (10 cc each collection)
- Urine biomarkers (during hospitalization only)
 o Baseline, Day 7 and Day 14 (5 cc each collection)
- Medical/Medication history
- Study medication dosing
- AE and SAEs
- Concomitant medications and COVID-19 specific treatment other than vitamins and minerals
- Modified SOFA, daily until discharge, & at Day 7, 14, and 28, with discharged patients receiving a score of 0 and deceased patients receiving a score of 20.
- NIAID-OS, daily and until discharge and at Day 7, 14, and 28
- For patients who are discharged, before or after completing 14 days of in-hospital treatment, a phone visit at day 7, 14, and 28 after randomization will be conducted to collect serious adverse events and NIAID-OS score.

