5.2. Assessment of Safety

- Incidence of adverse events (AEs)
- Incidence of serious AEs (SAEs)
- Incidence of thromboembolic events
- Creatinine, bilirubin, AST and ALT, hemoglobin

In addition to the ongoing and final safety assessments through the course of the trial, a detailed review of safety by the DSMB will follow the ascertainment of the 14-day outcomes on the first 30 and 120 patients. After 30 and 120 patients have received treatment and have completed their day 14 event, enrollment will be suspended (suspension of enrollment will occur at n = 30, based on DSMB recommendation, enrollment will continue during the safety analysis at n = 120). An interim blinded safety report will be sent to the DSMB. Enrollment will continue according to DSMB recommendations. The DSMB will provide a report to the UTHealth COVID-19 Research Workgroup and UTHealth IRB to consider further patient screening and enrollment.

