11.3. Eliciting Adverse Event Information

The investigator is to report all directly observed AEs and all AEs spontaneously reported by the patient. Patients will be questioned daily about AEs if they are able to respond, and then followed through the duration of the study.

[figure not shown]

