11.4. Reporting

Each AE is to be classified by the investigator as serious or non-serious.

All AEs that occur in study subjects during the AE reporting period specified in the protocol must be reported, whether or not the event is considered to be related to study drug.

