11.4.1. Reporting Period

The AE reporting period for this study begins upon initiation of study drug and ends up to 16 days after randomization (14 days of drug dosage plus two days), while SAEs will be continued to be reported up to Day 28, and will be assessed via follow-up, or through the patient's chart. However, AEs considered secondary to protocol mandated procedures should be reported post signing of the informed consent form (ICF), whether or not they occur before or after initiation of study drug. Subjects discharged from the hospital will be contacted on day 7, 14, and 28 to assess for SAEs. In addition, SAEs that occur during the protocol-defined AE reporting period that the investigator assesses as unexplained and related to the study drug will also be reported as an SAE to the UTHealth IRB and the FDA. AEs and SAEs that occur after the protocol-defined period that the

investigator assesses as related to the study drug will also be reported as an AE to UTHealth. If the event is serious, related, and unexpected, the event will be reported to the investigator IRB and the FDA.

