11.4.2. Reporting AEs

All AEs (serious and non-serious) are to be reported on the AE CRF in the clinical database during the AE reporting period as described in Section 11.1.

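### No stated procedure elicits non-serious adverse events after discharge, although the protocol's AE window runs to day 16; the crude AE comparison may therefore depend on length of stay

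*Combined protocol and SAP*

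**What the plan says.** The reporting rule is broad. Section 11.4 of the combined protocol and SAP states that "All AEs that occur in study subjects during the AE reporting period specified in the protocol must be reported", and section 11.4.2 repeats it: "All AEs (serious and non-serious) are to be reported on the AE CRF in the clinical database during the AE reporting period". Neither makes an exception for discharged patients. Section 11.4.1 starts the period at the first dose and says that it "ends up to 16 days after randomization (14 days of drug dosage plus two days"; SAE reporting continues to day 28.

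The collection procedure for discharged patients is narrower. Section 8.4 provides that "a phone visit at day 7, 14, and 28 after randomization will be conducted to collect serious adverse events and NIAID-OS score". Section 11.4.1 agrees: "Subjects discharged from the hospital will be contacted on day 7, 14, and 28 to assess for SAEs". Section 8.4 also stops the creatinine and hemoglobin collection that follows the last dose once the patient leaves hospital.

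On elicitation in general, section 11.3 has investigators report what they observe and "all AEs spontaneously reported by the patient". It adds: "Patients will be questioned daily about AEs if they are able to respond, and then followed through the duration of the study". It does not say what following consists of after discharge.

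AE incidence is the first safety outcome in section 5.2. Time to discharge is one of the other outcomes in section 5.1.3. Discharge before day 14 ends dosing (sections 7.4.2 and 10). Section 13 gives no safety analysis that allows for time at risk or uses a common window.

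**The concern.** If the calls are made as sections 8.4 and 11.4.1 describe them, non-serious events are actively sought only while the patient is in hospital. Two consequences need to be kept apart.

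The first does not depend on any treatment effect: against a window that runs to day 16, non-serious AEs are under-counted in both arms. The second is conditional. Length of stay is fixed after randomization and the drug may change it. If stays differ by arm, the arms are observed for unequal times, and a plain proportion with an AE can be lower in the arm discharged sooner for that reason alone. A longer stay on vadadustat would push the comparison the other way.

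The incomplete counts would also enter the DSMB's reviews of 14-day safety (section 9). The events exposed to this are non-serious ones, including laboratory abnormalities not classed as serious.

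**Working it through.** **Text, side by side**

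| Question | Reporting rule | Procedure after discharge |
|---|---|---|
| Which events? | All, serious and non-serious (11.4, 11.4.2) | SAEs, plus NIAID-OS in 8.4 (8.4, 11.4.1) |
| Until when? | Up to day 16; SAEs to day 28 (11.4.1) | Calls at days 7, 14 and 28 (8.4, 11.4.1) |
| How? | Daily questioning, spontaneous reports, undefined following (11.3) | No stated step that elicits non-serious AEs |

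The conflict needs no arithmetic. The documents give no AE incidence or expected length of stay, so there is no planned figure to reproduce. What follows is an illustration on assumed inputs.

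**Assumptions (none from the documents).** Length of stay is exponential with mean m days. The hazard of a first non-serious AE is h per day in hospital, the same in both arms, and g per day after discharge. Recording stops at discharge. The horizon is 16 days. Write s = h + 1/m.

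**Recorded incidence** = (h/s) × [1 − exp(−16s)]. With h = 0.05:
- m = 8: (0.05/0.175) × [1 − exp(−2.8)] = 0.2857 × 0.9392 = 26.83%
- m = 6: (0.05/0.2167) × [1 − exp(−3.467)] = 0.2308 × 0.9688 = 22.36%
- Gap: 26.83 − 22.36 = 4.47, or 4.5 points

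**Incidence with complete capture to day 16** = 1 − {exp(−16s) + (1/m) × exp(−16g) × [1 − exp(−16(s − g))]/(s − g)}. For example, m = 8 and g = 0.02 give 1 − {0.0608 + 0.125 × 0.7261 × 0.9163/0.155} = 1 − 0.5974 = 40.3%. When g = h = 0.05, the expression reduces to 1 − exp(−0.8) = 55.1%.

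| Hazard after discharge, g | Complete capture, 8 v 6 days | Gap that is real | False part of the 4.5 points | First events missed, 8 v 6 days |
|---|---|---|---|---|
| 0 | 26.8% v 22.4% | 4.5 | 0 | 0% v 0% |
| 0.01 | 34.0% v 30.7% | 3.3 | 1.2 | 21% v 27% |
| 0.02 | 40.3% v 38.0% | 2.3 | 2.2 | 33% v 41% |
| 0.05 | 55.1% v 55.1% | 0 | 4.5 | 51% v 59% |

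A real gap here is one that follow-up of everyone to day 16 would also show, because the arm discharged sooner spends fewer days at the in-hospital hazard.

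**Sensitivity.** For the same stays, the recorded gap is 12.4% − 10.2%, about 2.3 points unrounded, at h = 0.02, and 43.2% − 37.0%, about 6.3 points unrounded, at h = 0.10. A smaller difference in stay, 8 v 7 days at h = 0.05, gives 26.8% v 24.7%. If stays do not differ, the formula gives the same value in both arms: there is no between-arm bias, only under-counting.

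**The case against.** The strongest reply is that capture after discharge is loosely specified rather than absent. Spontaneous reports are recorded. Section 11.3 follows patients for the whole study. Section 8.4 lists AEs and SAEs as a collection item without the hospital-only limit that it puts on biomarkers. The daily record review for thromboembolic events in section 11.1 has no stated end at discharge. Section 8.3 describes wider contacts, but only for patients who stop drug, and times them from discharge rather than randomization. Appendix 1, to which section 8.4 defers, is not in the text available, and section 11.8 points to a Manual of Procedures for further safety detail. All of this stands. A reader might infer that no non-serious event is recorded after discharge, and the documents do not support that. They do, however, twice describe the calls as SAE contacts, and they name no other step that asks about non-serious events.

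A second reply is that the window may mean last dose plus two days, so that for a patient discharged early the gap is about two days. The wording allows this reading, although it counts from randomization. It would not remove the problem: no step elicits non-serious events in those two days either, and the window itself would then vary with length of stay.

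Third, the important events are largely protected. SAEs are collected to day 28, section 11.2 treats doubtful cases as serious, and most of the thromboembolic events listed in section 11.1 would qualify. This stands and limits the point to non-serious events.

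Fourth, dosing stops at discharge, so a lower count may partly reflect less exposure. This also stands, and it is why the false part of any gap cannot be fixed at one value.

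**Conclusion.** The conflict holds on the text: the reporting rule covers all AEs to day 16, while the described calls cover SAEs. Followed as written, the plan under-counts non-serious AEs against its own window whenever such events occur after discharge and are not volunteered.

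The between-arm bias is possible rather than established. It needs stays to differ by arm and some AE hazard after discharge. A reader might infer that the arm discharged sooner will look safer, that a false advantage of 2 to 4 points is to be expected, or that about half of all events are lost. The documents support none of these. They give no stays or AE rates, and those sizes require the in-hospital hazard to continue unchanged after dosing has stopped. In the illustration (8 v 6 days, 5% per day in hospital), the recorded gap is 4.5 points and its false part lies anywhere from none to all of it.

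The change should be made because it is cheap and removes the dependence on stay. It does not put the SAE comparison in doubt. Confidence is moderate, because Appendix 1 could show that the calls already cover all AEs; sections 8.4 and 11.4.1 would then still need to be reconciled with it.

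**What to change.** In sections 8.4 and 11.4.1, have the existing day-7 and day-14 calls ask about all AEs, including thromboembolic events, since the last contact. A day-14 call cannot cover days 15 and 16, so have the day-28 call ask back to day 16 for non-serious AEs. State in section 11.3 what following a patient after discharge consists of, and align section 8.3 and Appendix 1 with it.

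In section 13, add AE incidence for the in-hospital period separately and AEs per patient-day of observation. With a constant in-hospital hazard, the per-day rate is equal in the two arms when there is no true difference (0.05 per day in the illustration). If the hazard falls during the stay, that no longer holds exactly, so this table supplements the added questions and does not replace them.

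If elicitation after discharge is not added, label the non-serious AE endpoint as in-hospital only and reconcile it with the day-16 window.

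The cost is a few more questions on calls already scheduled and additional safety tabulation. The downside is that non-serious events reported by phone are less reliable than those seen in hospital, and recall is longer at day 28.

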8.4.1. Extended Follow Up

Eligible patients will be asked on the consent form if they would like to consent to participate in an extended follow up opportunity which will consist of the following:

- Return to the clinic at 6, 12 and 24 months
- Complete a quality of life questionnaire
- Provide a small blood sample (10 ml)
- Provide a urine sample (10 ml)
- Perform a pulmonary function test to see how well their lungs are working and a bedside echocardiogram to see how their heart is working.

The participant will receive a \$100 gift card for each follow up visit completed. In addition, the parking and travel expenses will be covered.

To consent to the optional long term follow up, the patient will be asked to check a box and initial.

8.5 Protocol Deviations: Protocol deviations will be recorded in the RedCAP database. The type of deviation will be specified. The deviation will be described and corrective actions will be recorded.

9. Data and Safety Monitoring Board (DSMB)

A DSMB will be formed. DSMB is a group of external experts who will provide oversight to the conduct of the study and provide safety assessment through planned interim analysis. The DSMB shall include an odd number of members, minimum of 3, preferably 5. It should include at least one of the following: one critical care physician, one physician-trialist and one statistician.

In addition to the ongoing and final safety assessments through the course of the trial, a detailed review of safety by the DSMB will follow the ascertainment of the 14-day safety on the first 30,120 and 400 patients. After 30,120 and 400 patients have received treatment and have completed their day 14 event, an interim blinded safety analysis by the DSMB will be completed. The DSMB will provide a report to the UTHealth COVID-19 Research Workgroup and UTHealth IRB to consider further patient screening and enrollment. In the n=400 safety analysis there will be no planned suspension in ongoing recruitment during evaluation of the findings.

10. Discontinuation of study treatment in individual patients (Stopping Criteria)

Vadadustat must be permanently discontinued if a patient meets one of the following pre-specified criteria:

1.	Patient completes 14 days of in-hospital treatment since randomization
2.	Patient is discharged before 14 days of treatment since randomization
3.	If the clinical team deems necessary that the patient receive a medication that was previously prohibited, or if the clinical team decides the patient should not receive vadadustat.
4.	Persistent eGFR decrease (greater than 2 days \leq 30)
5.	Hemoglobin above the gender specific upper limit of normal (ULN): females (16 g/dL) and males (18 g/dL)
6.	Patient dies

11. Safety Assessment 11.1. Adverse Events (AEs)

For the purposes of this study, an AE is any untoward medical occurrence (including an abnormal laboratory finding) that occurs in the protocol-specified AE reporting period; the event does not necessarily have a causal relationship with that treatment or usage.

An AE includes medical conditions, signs, and symptoms not previously observed in the subject that emerge during the protocol-specified AE reporting period, including signs or symptoms associated with pre-existing underlying conditions that were not present prior to the AE reporting period.

AEs therefore include the following:

- All AEs, whether suspected to be causally related to study drug or otherwise.
- All AEs secondary to any medication overdose, medication error, abuse, withdrawal, sensitivity, or toxicity.
- Illnesses apparently unrelated to study drug, including the worsening of a pre-existing illness (see paragraph below on Pre-existing Conditions).
- Injury or accidents. Note that if a medical condition is known to have caused the injury or • accident (for example, a fall secondary to dizziness), the medical condition (dizziness) and the accident (fall) will be reported as 2 separate AEs.
- Abnormalities in physiological testing or physical examination findings that require clinical • intervention or further investigation (beyond ordering a repeat [confirmatory] test).
- Laboratory abnormalities that require clinical intervention or further investigation (beyond ٠ ordering a repeat [confirmatory] test) unless they are associated with an already reported clinical event. Laboratory abnormalities associated with a clinical event reported as an AE (for example, elevated liver enzymes in a subject with jaundice) will be described under 'Comments' on the report of the clinical event rather than reported as separate AEs.

The following guidelines are to be used when reporting AEs for this study:

- Medical Diagnoses Whenever possible, a medical diagnosis term will be used to report AEs instead of signs and symptoms due to a common etiology, as determined by qualified medical study staff. For example, pneumonia will be the reported AE term, instead of fever, dyspnea, etc., when the diagnosis has been established. Signs and symptoms will be reported as event terms only when the medical diagnosis remains unknown and revised to a medical diagnosis term once it has been established.
- **Procedures** Diagnostic and therapeutic noninvasive and invasive procedures, such as • surgery, will not be reported as AEs. However, the medical condition for which the procedure was performed will be reported if it meets the definition of an AE. For example, an acute appendicitis that begins during the AE reporting period will be reported as the AE and the resulting appendectomy noted under "Comments."
- Preplanned therapeutic procedures not associated with a new medical condition or ٠ worsening pre-existing condition will not be reported as AEs.
- Pre-existing Conditions In this study, a pre-existing condition (i.e., a disorder present • before the AE reporting period started and noted on the pretreatment medical history/physical examination form) will not be reported as an AE unless the condition worsens, or episodes increase in frequency during the AE reporting period.
- Abnormal Test Findings All laboratory test results will be reviewed by the research • team. The research team will utilize his/her judgment in determining if out of range laboratory values are clinically significant. Laboratory tests that are considered clinically significant will be reported as AEs, either separately or as part of a description of a symptomatic AE. If there are significant changes in a laboratory report from a previous result that are determined to be clinically significant, these will also be reported as AEs. Any abnormal laboratory value, which requires treatment or further diagnostic testing or results in discontinuation from study will be reported as AEs. An expected laboratory

abnormality from a condition that is part of the medical history is not considered clinically significant for the purposes of the study unless it represents a worsening of the condition.

Special daily safety monitoring for the risk of thrombosis and proinflammatory state is planned in this trial. This will be achieved by daily review of electronic medical records for clinical evaluation of thromboembolic events. Furthermore, all patients will be managed according to local institutional anticoagulation protocols.

Thrombo-embolic events (complications) including:

- Deep vein thrombosis—catheter associated or spontaneous
- Pulmonary embolism
- Ischemic stroke
- Systemic arterial thrombosis
- Acute coronary syndrome/myocardial infarction.

11.2. Serious adverse events (SAEs)

SAEs are AEs that meet one or more of the following criteria/outcomes:

- Death
- Life-threatening
- In-patient hospitalization or prolongation of existing hospitalization
- Persistent or significant disability/incapacity
- Congenital anomaly/birth defect
- Is considered a medically important event not meeting the above criteria, but which may jeopardize a patient, or may require medical or surgical intervention to prevent one of the criteria listed in this definition

Serious also includes any other event that the investigator judges to be serious. If there is any doubt whether the information constitutes an AE or SAE, the information is to be treated as an SAE.

Life threatening – Defined as any event in which the subject was at risk of death at the time of the event. 'Life threatening' does not refer to an event which hypothetically might have caused death if it were more severe. For example, drug-induced hepatitis that resolved without evidence of hepatic failure would not be considered life threatening, even though drug-induced hepatitis of a more severe nature can be fatal.

Hospitalization – Defined as an overnight admission with observation of a minimum of 24 hours. A hospitalization planned before the start of the study for a preexisting condition that has not worsened during the AE reporting period does not constitute an SAE unless an untoward event occurs related to the procedure (e.g., elective hospitalization for a total knee replacement due to a pre-existing condition of osteoarthritis of the knee that has not worsened during the study).

Disability – Defined as a substantial disruption in a person's ability to conduct normal life functions.

In addition to the above criteria for classifying AEs as serious, the following situations will be also be classified as serious for purposes of this study:

Malignancies – If a subject develops basal cell carcinoma of skin, squamous cell carcinoma of skin, or cervical carcinoma in situ during the study, or has worsening of these events from baseline, the investigator will determine if the event is reported as an AE or SAE. Newly diagnosed malignancies or a recurrence of a malignancy will be reported as an SAE with the seriousness criterion "medically important" if no other seriousness criteria are met.

All cardiac events will be specifically elicited and followed. Troponins ordered by the clinical team will be recorded in the Daily lab section of the CRF. Troponin levels are not required, but will be recorded when available. Recent data using vadadustat in the PROTECT2 study showed an increase rate of major adverse cardiac events (MACE) in some study participants. This increase in MACE events occurred in patients who were not on dialysis, were treated outside the US and were treated for more than 6 months with vadadustat. This risk as not seen in dialysis patients and was not seen in study participants in the US. The DSMB was notified of these results. Based on the above data, the DSMB recommended that all cardiac events be tracked and troponins be recorded when ordered by the treating team.

Any SAE, regardless of causal relationship, must be reported to the sponsor within 24 hours after the Investigator becomes aware of the SAE. Compliance with this time requirement is essential so that sponsor may comply with its regulatory obligations.

